#### 7.10. Volume of Blood Collection

The approximate blood volume collected from each individual during the study will be as follows:

Phase A Assessment	Number of Collections*	mL/Collection	Total (mL)
Chemistry	3 or 4	5	20ml
BNP	3 or 4	5	20 ml
Hematology	3 or 4	5	20ml
Coagulation	3 or 4	3	12ml
Angll/Ang 1-7	6	105	6025
SOD2 Activity	5	2	10
Serum nitric oxide	5	(see SOD2)	
Isoprostanes/Isofurans	5		
Pk	3	5	15
immunogenicity	2	5	10
	≈192		

\*Number of collections depends upon whether samples are taken both at screening and baseline.

Phase B	Number of			
Assessment	Collections*	ml/collection	Total (ml)	
Chemistry	6 or 7	5	35	
BNP	6 or 7	5	35	
Hematology	6 or 7	5	35	
Coagulation	6 or 7	5	35	
Serum nitric oxide	7 or 8	2	16	
SOD2/Cytokines/	7 or 8	5	40	
isoprostanes/isofurans	Cytokines (4)			
AngII/Ang 1-7	7 or 8	10	80	
RNA	1	5	5	
Lymphocytes	1	8	8	
pK	3	5	15	
	Total blood ve	304		

Number of collections depends upon whether samples are taken both at screening and baseline.

#### 7.111. Prior and Concomitant Medications

Medications (prescription, over-the-counter, and herbal) and nutritional supplements taken during the 30 days prior to dosing and medication taken for the treatment of PAH during the 12 weeks prior to dosing will be reviewed and recorded at screening. At the first Baseline visit, current medications will be recorded. At each subsequent Treatment, or Early Discontinuation visit (if applicable), the change in medications since the previous visit will be recorded.

## 7.12 Screening and Baseline

# 7.12.1 Screening

Screening procedures (unless otherwise specified below) must be performed no more than 90 days prior to the first dose of study drug. Results from some screening procedures which are performed no more than 7 days prior to the first dose of study drug, as specified below and in Appendix 1 can also be used as baseline values. In Phase B, there must be a minimum of 10 days and a maximum of 18 days between screening/baseline visit and date of first study drug administration.

Prior to performing any study-related assessments, the Investigator will inform the patient, orally and in writing, about the potential benefit and any risks associated with the participation in this trial.

After having given their informed consent in writing, subjects will undergo the following screening evaluations:

- General medical and drug history, including recording of demographic data; concomitant diseases; review of medication(s) or investigational products taken or investigational devices used in the past 30 days and medications taken for the treatment of PAH in the 12 weeks prior to enrollment; and complaints/symptoms for baseline safety evaluation.
- Physical examination (including body weight and height)
- WHO classification
- BP (systemic BP is taken after 5 minutes seated and again after 5 minutes standing)
- Pulse oximetry and heart rate
- Pregnancy test (urine) in females of childbearing potential

- Blood samples taken for standard clinical laboratory tests (hematology, chemistry, and coagulation panel)
- Urinalysis
- If the subject has not had a 6MW test with documented results within three
  months (12 weeks) prior to screening, administer the 6MW test, followed by Borg
  dyspnea scoring. If the 6MW test and Borg dyspnea score is performed at
  screening, the results can also be used for baseline assessments and that test
  will not have to be repeated at baseline..
- Provide instructions to fast for 2 hours prior to the baseline visit and bring in first morning urine void on ice for urine assessment of biomarkers.

#### 7.12.2 Baseline

The following baseline assessments must be performed prior to the first dose of study drug unless otherwise specified below.

- Change since screening in medical history or physical exam, including concomitant diseases; medication(s) or investigational products taken or investigational devices used; WHO classification; and complaints/symptoms for baseline safety evaluation.
- BP (systemic BP is taken after 5 minutes seated and again after 5 minutes standing)
- Pulse oximetry and heart rate
- Pregnancy test (urine) in females of childbearing potential\*
- Urine and blood samples taken for standard clinical laboratory tests (hematology, chemistry, urinalysis, and coagulation panel\*
- Urine (first morning void, on ice) and blood samples taken for biomarker assessments as outlined in Appendix 1 and 2
- ECG
- Echocardiogram
- Assessment and recording of any SAEs and study-related issues (if any) since signing of the Informed Consent Form

- Recording of current concomitant medications
- Instruct subjects to bring in first morning void to follow-up visit\*\*\* in two weeks.
- \* **Note:** Results obtained at screening for the indicated assessments may be counted as baseline values if assessment was performed no more than 7 days prior to the first dose of study drug.

Results of standard laboratory tests must be available and reviewed before start of treatment.

# 8.0 Study Treatment

rhACE2 will be administered intravenously at a slow infusion at a rate of 1ml/minute for approximately 30 minutes.

The individual amount of rhACE2 and corresponding volume will be calculated as:

- Volume rhACE2 (ml) = Body weight (kg) X dose (mg/kg)/ concentration (5.2 mg/ml)
- Add 30ml-calculated volume rhACE2 to physiological solution of NaCl to reach 30ml infusion solution.

**rhACE2** is produced by Glaxo Smith Kline. The drug is stored in a controlled environment and will be shipped with a certificate of analysis. Temperature will be recorded until delivery to the clinical center. Shipment and long term storage at <-20 °C.

#### 9.0 Risks

# 9.1 Risks of Study Drug:

It is possible that rhACE2 treatment alone, or when combined with other medications used to treat PAH, will lower systemic BP in pulmonary arterial hypertension patients. The first participants (initial single- dose subjects) will be admitted for study drug administration and monitored for 24 hours after drug administration. Subsequent multidose subjects will be admitted for the entire 6 day dosing course and will be monitored for 5 hours after their last dose of rhACE2.

#### 9.2 Risks of Study Procedures:

9.2.1 Risks of Blood Draw: Pain, redness, soreness, bruising, or infection may occur at the needle stick site. Rarely some people faint.

- 9.2.2 Pulmonary arterial catheters will only be placed for clinical indications, thus there is no increased risk associated with this procedure compared to usual clinical care
- 9.2.3. Risks of echocardiography: some patients experience minor discomfort with the procedure for proper placement of the ultrasound probe.

# 10 Reporting of Adverse Events or Unanticipated Problems involving Risk to Participants or Others

# 10.1 Adverse Event Terminology

#### 10.1.1 Adverse Event

An AE is "any untoward medical occurrence in a patient or clinical investigation subject administered a pharmaceutical product and which does not necessarily have a causal relationship with this treatment". An adverse event can therefore be any unfavorable and unintended sign (including an abnormal laboratory finding), symptom, or disease temporally associated with the use of a medicinal (investigational) product, whether or not considered related to the medicinal (investigational) product.

AEs include any of the following:

- Worsening (change in nature, severity or frequency) of conditions present at the onset of the trial
- Subject deterioration due to the primary illness
- Intercurrent illnesses
- Drug interactions
- Events related or possibly related to concomitant medications
- Abnormal laboratory values or changes of vital signs, as well as significant shifts from baseline within the range of normal, which the Investigator considers to be clinically significant

#### 10.1.2 Adverse Drug Reaction

In the pre-approval clinical experience with a new medicinal product or its new usage, particularly as the therapeutic dose(s) may not be established, an adverse drug reaction is defined as:

All noxious and unintended responses to a medicinal product related to any dose should be considered adverse drug reactions (ADR).

# 10.1.2.1 Unexpected Adverse Drug Reaction

An unexpected ADR is:

An adverse drug reaction, the nature or severity of which is not consistent with the applicable product information, also known as reference safety information. For rhACE2, an investigational medicinal product, the reference safety information is the Investigator's Brochure\*\*.

## 10.1.3 Serious Adverse Event/Serious Adverse Drug Experience

During clinical investigations, serious AEs may occur. If the event is suspected to be drug-related, the event may be significant enough to lead to important changes in the way the medicinal product is developed (e.g. change in dose, population, needed monitoring, consent forms). This is particularly true for reactions, which, in their most severe forms, threaten life or function.

A serious AE (SAE) or serious adverse drug experience (SADE) is any untoward medical occurrence that:

- · Results in death.
- Is life-threatening. 'Life-threatening" refers to an event in which the subject is at
  risk of death at the time of the event; it does not refer to an event which
  hypothetically might have caused death if it were more severe (ICH E6).
- Requires inpatient hospitalization or prolongation of existing hospitalization.
- Results in persistent or significant disability/ incapacity (as per reporter's opinion).
- Results in a congenital anomaly/birth defect.
- Causes another medically important condition. Important medical conditions that may not result in death, be life-threatening or require hospitalization may be considered as SAEs or SADEs when, based upon appropriate medical judgment, they may jeopardize the subject or may require intervention to prevent one of the outcomes listed in the definition above. Examples of such events are intensive treatment in an emergency room or at home for allergic bronchospasm; blood dyscrasias or convulsions that do not result in hospitalization; or development of

drug dependency or drug abuse [Code of Federal Regulations Title 21, Volume 5, 21CFR312.32, revised April 1, 2006].

Please note: Serious is not synonymous with severe. An event may be severe (e.g., severe headache) but still be of minor medical significance. Serious refers to an event that poses a threat to the subject's life or functioning.

## 10.1.4 Assigning Severity to an Adverse Event

Mild: Causing no limitation of usual activities:

the subject may experience slight discomfort.

Moderate: Causing some limitation of usual activities;

the subject may experience annoying discomfort.

Severe: Causing inability to carry out usual activities;

the subject may experience intolerable discomfort or pain.

#### 10.1.5 Assigning Relationship of Adverse Event to Study Drug (Causality)

The Investigator will determine the relationship of each AE to study drug (i.e., causality) by using the classification criteria 'not related', 'possibly related', or 'probably related'. Descriptions of the three classification categories are as follows:

#### 10.1.6 Not Related

Exposure to study drug has not occurred; administration of study drug and the adverse event are not reasonably related in time; or the AE is considered by the Investigator to be due to a pre-existing condition, a known manifestation of the target disease, a recurrent condition, or is likely explained by environmental or diagnostic therapeutic factors or was pre-existing and did not deteriorate.

#### 10.1.7 Possibly Related

The AE occurred during or within a reasonable period of time after administration of the study drug, or a pre-existing event worsened within an appropriate period of time after administration of study drug, but the AE could be explained equally well by factors or causes other than exposure to the study drug.

This category will also be used if there is a lack of information, or insufficient or conflicting evidence exists for classifying the causality of the AE.

# 10.1.8 Probably Related

The AE occurred during or within a reasonable period of time after administration of the study drug or a pre-existing event worsened within an appropriate period of time after administration of study drug, and at least one of the following criteria is applicable:

- the event could not be explained by the clinical condition or history of the subject, environmental or toxic factors, or other diagnostic or therapeutic measures;
- the event was an expected ADR associated with study treatment or a classlabeled drug effect;
- the AE subsided or disappeared after withdrawal or dose reduction of study treatment; or
- the AE recurred after re-exposure to study treatment.

# 10.2 Adverse Event Recording and Reporting

## 10.2.1 Adverse Event Recording

At baseline, all SAEs and study-related AEs since signing of the Informed Consent Form will be recorded. After initial study drug administration, all AEs will be recorded.

Each AE occurring to a subject, either spontaneously revealed by the subject or observed by the Investigator, whether believed by the Investigator to be related or unrelated to the study drug, must be recorded on the AE Case Report Form and on the subject's file.

Type and severity of AEs will be reported by the subjects without being given a list of fixed symptoms beforehand.

The Investigator will also determine the relationship of any AE to study drug (causality) and record it on the appropriate section of the AE CRF as well as their severity, time of onset, duration, and the precautions carried out, and whether or not the event meets one or more of the definitions of an SAE.

Laboratory results will be recorded on the case report form and the investigator will indicate whether abnormal results (high or low) are clinical or not clinically significant. Clinically significant laboratory abnormalities will be entered on the 'Adverse Event Form' of the CRF. Clinically significant changes in vital signs (e.g., tachycardia) or other clinically significant changes observed by the physician will be entered in the appropriate CRF. These AEs will also be noted on the 'Adverse Event Form' of the CRF as well as in the subject file.

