#### Objectives:

#### 2.1 Primary Objective

The primary objective of the study is to determine safety of rhACE2 when administered as a single dose or multiple doses intravenously to subjects with PAH receiving background PAH-specific therapy.

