#### 4.0 Study Design:

This is a Phase 1, single center, open-label, dose-escalation in subjects with PAH whose symptoms have been clinically stable for 8 weeks prior to enrollment and have had no change in PAH-specific therapy 12 weeks prior to enrollment. Eligible subjects will undergo baseline assessments before beginning treatment with rhACE2.

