- Hypotension as defined by mean arterial pressure <60mmHg or a drop in systolic blood pressure of 25%
- Changes in echocardiogram suggesting worsening right ventricular function rhACE2 will be administered in the Cardiac Catheterization lab or the Cath lab holding area where the participant will be monitored for 4 hours following dosing with pulmonary arterial catheter in place. After four hours, the catheter will be removed. Transpulmonary blood will be collected from the mixed venous position and the wedge position at baseline and four hours after drug administration prior to removal of the catheter. Study participants will then be admitted to the Clinical Research Center (CRC) for further monitoring for a total of 24 hours post dosing. Hemodynamics will be measured at time points described in the schedule of events. After 24 hours from drug administration, patients will be discharged from the CRC. For each dosing group, an acceptable safety profile at each dose level will be required prior to dose escalation. In addition, the safety profile of the planned dose-escalation regimen will be evaluated throughout the study. Subjects will return after a two-week washout period for follow-up assessments.

Enrollment will continue until 12 subjects have completed the washout period and followup assessments.

If no safety concerns have been identified in the dose escalation phase, the multiple phase dosing will proceed as described below using one dose below the maximal tolerated dose of the single dose phase or at 1.2mg/kg if no MTD is reached.

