#### Exclusion Criteria

- Previous treatment with any formulation of rhACE2.
- Known allergy or hypersensitivity to rhACE2.
- History of systemic hypotension, defined as systolic BP < 90 mm Hg and/or diastolic BP <60 mm Hg.

- Hospitalization for PAH associated deterioration in the previous 6 months
- Use of any investigational product or device within 30 days prior to dosing, or known requirement for any investigational agent prior to completion of all scheduled study assessments.
- Known to be positive for human immunodeficiency virus (HIV), Hep B, or Hep C or with cirrhosis from any cause.
- Any additional medical condition, serious intercurrent illness, or other extenuating circumstance that, in the opinion of the Investigator, may significantly interfere with study compliance, including all prescribed evaluations and follow-up activities.
   Concurrent disease or condition that may interfere with study participation or safety include bleeding disorders, arrhythmia, organ transplant, organ failure, current neoplasm, poorly controlled diabetes mellitus, and serious neurological disorders.
- Complex congenital heart disease
- Estimated GFR <60mL/min/1.73m² or hepatic enzyme levels more than 2 times the upper limit of normal.
- Pregnant or lactating at screening, or planning to become pregnant (self or partner) at any time during study.
- Weight >75kg.
- Any bleeding concerns as evidenced by INR > 1.5 (in patients not receiving anticoagulation therapy) or platelet count < 80,000

- Hematocrit < 30%

- Any use of an ACE inhibitor or angiotensin receptor blocker within 7 days of enrollment

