#### 7.5 Electrocardiogram

In subjects with PAH, the electrocardiogram (ECG) typically reveals right axis deviation and right ventricular (RV) hypertrophy. The standard 12-lead ECG will be recorded while the subject is resting in supine position. The following parameters will be assessed: HR, RR, PQ, QRS, QT and QTc. Additionally, the occurrence of de- or repolarization disorders, arrhythmic disorders or other abnormalities will be assessed and obvious changes of ECG parameters compared to the baseline record will be commented upon. ECGs will be interpreted locally. Changes to the ECG will be coded by the Investigator as clinically significant or not clinically significant. Clinically significant changes will be reported as AEs. Original printouts will be archived within the subject file and ECG recording results will be noted in the subject's CRF.

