# 12 Statistical Considerations

Descriptive statistics will be used to characterize patients at study entry. Dose analysis will be approached using the design below to determine the dose limiting toxicity (DLT). No statistics will be performed specifically on tolerability data. Instead, AEs will be described in their entirety and evaluated by descriptive statistical methods. Despite sample size limitations that hamper statistical inference, analysis of secondary endpoints will be conducted using mixed-effects regression modeling techniques, supported by conditional estimation methods with interaction. For example, the change in pulmonary and systemic hemodynamic measurements according to echocardiogram from baseline to end of study, the change in six minute walk distance (6MWD) from baseline to end of study, and the change in biochemical variables (BNP, NO and SOD2) from baseline to Day 6 and end of study will be assessed to determine the delta in paired comparisons over time.

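### Section 12 describes adverse events only and plans no change-from-baseline summary of routine laboratory or ECG data, so these data enter the safety results only through the unblinded investigator's judgement of clinical significance

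*Combined protocol and SAP*

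**What the plan says.** Section 2.1 sets the aim: "The primary objective of the study is to determine safety of rhACE2". Section 4.0 gives the design: "This is a Phase 1, single center, open-label, dose-escalation in subjects with PAH". It describes no control arm. Phase A has four dose levels of three subjects: "Enrollment will continue until 12 subjects have completed the washout period".

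Four sections govern what happens to laboratory and ECG results.

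- **10.1.1 (AE definition).** Abnormal laboratory values and vital-sign changes can be AEs, and so can "significant shifts from baseline within the range of normal, which the Investigator considers to be clinically significant".
- **10.2.1 (recording).** All laboratory results go on the CRF. Then "the investigator will indicate whether abnormal results (high or low) are clinical or not clinically significant". Abnormalities rated significant move to the AE form. The section also provides for other clinically significant changes that the physician observes.
- **7.5 (ECG).** "Changes to the ECG will be coded by the Investigator as clinically significant or not clinically significant". The significant ones become AEs. Obvious changes from the baseline tracing are to be commented on, and results are noted in the CRF.
- **12 (statistics).** No statistics are planned for tolerability. "Instead, AEs will be described in their entirety and evaluated by descriptive statistical methods". Other descriptive statistics are for study entry. The modelled changes from baseline are for secondary endpoints; the examples given are echocardiographic haemodynamics, 6MWD, BNP, NO and SOD2.

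Appendix 2 schedules chemistry, haematology and coagulation before dosing, at 24 hours and at 2 weeks, and ECG at baseline, 4 hours and 24 hours.

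**The concern.** The objective safety data pass through a subject-by-subject judgement before they reach any planned output, and the person making that judgement knows the dose. A modest shift shared by most subjects may look unremarkable in each one and show only when the paired changes are laid side by side. Section 12 asks for no such display.

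There is also a mismatch between two sections. A significant shift within the normal range meets the AE definition in 10.1.1, but the laboratory rating step in 10.2.1 puts the question only for high or low results.

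At stake is whether the report of a safety trial could be silent on a change in renal, hepatic, blood or ECG measurements that its own data contain. The plan gives secondary biomarkers such as BNP and SOD2 a paired analysis while giving the routine safety tests none.

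**Working it through.** The plan states no figure for this point, so there is nothing to reproduce. The check is a trace of the data flow, a count, and an illustration.

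**Data flow.** A laboratory result is recorded on the CRF. If high or low, it is rated. If rated significant, it goes on the AE form, and AEs are described under Section 12. A result that is not judged significant stays on the CRF and appears in no planned table. ECGs follow the same path, except that 7.5 already compares with baseline and uses no normal-range filter.

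**Count.** Section 7.8 lists 6 substrates + 5 electrolytes + 4 enzymes = 15 chemistry tests, 5 haematology tests and 2 coagulation tests, so 22 in all. BNP and troponin I are excluded because they are named secondary biomarkers. Then 22 × 2 post-dose times × 12 subjects = 528 values. Section 7.5 lists 6 ECG parameters: 6 × 2 × 12 = 144 more.

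**Illustration 1 (all inputs assumed).** Creatinine mean 0.75 mg/dL, between-subject SD 0.12, upper limit 1.1, and a 20% rise in every subject.
- New mean 0.75 × 1.2 = 0.90; new SD 0.12 × 1.2 = 0.144.
- P(above limit) = 1 − Φ((1.1 − 0.90)/0.144) = 0.082.
- Expected number above the limit: 12 × 0.082 = 0.99.
- P(none of 12 at one time point) = 0.918^12 = 0.36. For baseline means of 0.80 and 0.70 it is 0.11 and 0.65.
- Paired 95% limits for the ratio: exp(ln 1.2 ± 2.201 × CV × √2/√12). This gives 1.12 to 1.29 at an assumed within-subject CV of 8%, and 1.08 to 1.34 at 12%.

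**Illustration 2 (generic, also assumed).** Values normal, upper limit at +1.96 SD, the same upward shift in everyone.

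| Shift (SD) | P(above limit) | Expected of 12 | P(none of 12) |
|---|---|---|---|
| 0.5 | 0.072 | 0.87 | 0.41 |
| 1.0 | 0.169 | 2.0 | 0.11 |
| 1.5 | 0.323 | 3.9 | 0.009 |

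The paired 95% half-width in 12 subjects is 2.201 × s/√12, where s is the SD of within-subject change: 0.318, 0.477 and 0.635 for s = 0.5, 0.75 and 1.0. A mean shift of 0.5 SD is therefore clear of zero at s = 0.5, barely so at 0.75, and not at 1.0.

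**Multiplicity of the added intervals.** 22 tests × 2 times = 44 laboratory intervals. At 5% each, about 44 × 0.05 = 2.2 would exclude no change by chance. ECG adds 6 × 2 = 12, for 56 × 0.05 = 2.8 in total.

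**The case against.** A reader might infer that within-range laboratory shifts can never become AEs, or that one unblinded person alone decides which data count. The documents support neither. Section 10.1.1 expressly includes such shifts, and 10.2.1 has a route for other clinically significant changes. All laboratory results are on the CRF whatever their rating. Section 10.3 has an independent monitor review the CRFs after dose escalation and, if needed, carry out an interim safety analysis. The Supplemental Methods add that the Independent Safety Officer had full data at all times. The listed dose-limiting toxicities are only examples, so a laboratory or ECG toxicity could count as one.

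The entry limits are weak evidence of a range gap. Liver enzymes at the exclusion level ("hepatic enzyme levels more than 2 times the upper limit of normal") are high by definition, and platelets or haematocrit below the entry limits would ordinarily be reported low. The rating step already covers them, so only the reliance on judgement remains.

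The illustrations rest on assumed inputs and on one uniform shift, whereas doses run sixfold from 0.2 to 1.2 mg/kg. Even the central creatinine case gives a 64% chance (1 − 0.36) that at least one value prompts a rating. It is also tempting to read an interval that excludes no change as a drug effect. There is no control arm, and catheterisation, admission and about 192 mL of blood sampling in Phase A could move some values. Pooling over doses could also dilute a dose-related effect.

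These points stand and limit the claim. They do not supply the missing output: the monitor's role is advisory, and 10.3 specifies no tabulation. Supplemental Tables 4 and 6 are not in the text available, so laboratory results there cannot be ruled out, but a results table is not by itself a planned analysis.

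**Conclusion.** The point holds in limited form and is a cheap improvement. Section 12 specifies no change-from-baseline summary for routine chemistry, haematology, coagulation or ECG intervals. These data enter the planned safety results only through the unblinded investigator's judgement of significance. The laboratory rating step in 10.2.1 is narrower than the definition in 10.1.1. The monitor's CRF review mitigates the gap without closing it.

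The size that rests on the documents is the count: about 528 laboratory values and 144 ECG values in the planned 12 subjects, none with a specified summary. The creatinine and SD-shift figures only show that a consistent modest shift can produce few or no out-of-range values. They do not estimate any effect of rhACE2, and nothing here shows that a signal was present or missed.

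**What to change.** 1. **Reconcile 10.2.1 with 10.1.1.** Extend the CRF rating step to within-range shifts from the pre-dose value that the investigator considers significant, and print the pre-dose value beside each 24-hour and 2-week value. Tying the added step to the existing definition avoids having to rate every small change.
2. **Add descriptive tables to Section 12.** For each laboratory test and ECG interval, show per-subject change from baseline by dose and time, with a pooled mean change (log ratio where skewed) and 95% interval. Label the intervals descriptive: uncontrolled, unadjusted for multiplicity, and to be read with the by-dose profiles.
3. **Count subjects who cross the protocol's own entry limits after dosing**, whatever the investigator's rating: eGFR <60, liver enzymes >2 × ULN, platelets <80,000, haematocrit <30%. Name the eGFR equation. These counts are a reporting device and set no toxicity or stopping rule.

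The cost is some protocol and CRF wording and a few tables on data already collected. The downside is that some chance shifts will be listed, about 2 to 3 of the 56 pooled intervals, so the labelling in item 2 matters.
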